8. OTHER STATISTICAL ANALYSES

8.1. Other Efficacy Endpoints

8.1.1. Overview of Planned Efficacy Analyses

The other efficacy summaries and analyses will be based on the ITT population, unless otherwise specified.

Table 5 provides an overview of the planned efficacy analyses, with further details of data displays being presented in Appendix 13: List of Data Displays.

Endpoint	Change from Baseline[1]						
		Stats Ana	lysis	Summary Indiv		vidual	
	Т	F	L	Т	F	F	L
Responder FEV ₁							
Proportion of	Y			Y			Y
responders according							
to FEV ₁ (a responder is							
defined as a ≥100mL							
change in Trough FEV ₁							
from baseline) at Week							
4 and 8 [2]							
Trough FVC and IC	r	•	1			· · · ·	
Trough FVC	Y	Y		Y			Y
Trough IC	Y	Y		Y			Y
Rescue medication							
Mean number of puffs	Y			Y			Y
per day of rescue over							
the study duration							
(Weeks 1-8) captured							
using e-diary							
Percentage of rescue	Y			Y			Y
free days over the							
study duration (Weeks							
1-8) captured using e-							
diary [2]							
Mean number of				Y			Y
occurrences per day of							
rescue over the study							
duration (Weeks 1-8)							
captured using e-MDI				X			
Percentage of rescue				Y			Y
free days over the							
study duration (Weeks							
1-8) captured using e-							
	N/		T				
CAT score	Y	Y Y		Y			Υ

Table 5Overview of Planned Efficacy Analyses

Endpoint	Change from Baseline[1]							
		Stats Ana	lysis	Sum	mary	Indiv	Individual	
	Т	F	L	Т	F	F	L	
Proportion of CAT	Y			Y			Y	
responders [2]								
Inhaler assessments								
Inhaler ease of use	Y			Y			Y	
Inhaler errors				Y			Y	
E-RS								
E-RS	Y	Y		Y			Y	
Proportion of E-RS	Y			Y			Y	
responders [2]								

NOTES :

- T = Table, F = Figure, L = Listing, Y = Yes display generated.
- Stats Analysis = Represents TFL related to any formal statistical analyses (i.e. modelling) conducted.
- Summary = Represents TFL related to any summaries (i.e. descriptive statistics) of the observed raw data.
- Individual = Represents TFL related to any displays of individual subject observed raw data.
- 1. Analysis and Summaries to include absolute values too for all endpoints with the exception of Responder analysis
- 2. Summary and analysis will be combined into a single display.
- 3. Summary only

8.1.2. Planned Efficacy Statistical Analyses for Other Efficacy Endpoints

8.1.2.1. Responder FEV₁

Statistical Analyses for Proportion of Trough FEV₁ Responders Endpoints

• Proportion of responders according to FEV₁ (a responder is defined as a ≥100mL change in Trough FEV₁ from baseline)

Model Specification

- At each visit, the proportion of subjects achieving a ≥100mL change in Trough FEV₁ from baseline will be analysed using a generalised linear mixed model.
- The following covariates will be included in the model: period baseline, mean baseline, period, treatment, visit, visit by period baseline, visit by mean baseline and visit by treatment interactions, where visit is nominal.

Example SAS code

proc glimmix data=start; class subject period treatment visit; model endpoint(descending)=period treatment visit mean_base period_base visit*period_base visit*mean_base visit*treatment / dist=binary link=logit ddfm=kr solution; random intercept / subject=subject; random visit / subject=subject*period residual type=un; lsmeans visit*treatment / diff;

ods output Ismeans=Ismeans;

ods output diffs=diffs;

run;

Statistical Analyses for Proportion of Trough FEV₁ Responders

• Note: The residual statement turns the random statement into a repeated statement

Model Checking & Diagnostics

• Refer to Appendix 11: Model Checking and Diagnostics for Statistical Analyses.

Model Results Presentation

The odds ratio, 95% CI and p-value of UMEC/VI 62.5/25 vs. TIO/OLO 5/5 will be presented.

Summary Results Presentation

• The number and percentage of responders and non-responders at each visit will be summarized on the same table as the analysis results detailed above.

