FVC and IC at Week 4 and Week 8 will be analysed separately using the same methodology as that for the primary endpoint. The mean number of Inhalations of rescue medication per day for Weeks 1-2, 3-4, 5-6 and 7-8 will be analysed using a mixed model repeated measures analysis including covariates of period baseline, mean baseline, period, treatment, two-weekly period, two-weekly period by period baseline interaction and two-weekly period by mean baseline interaction. The model will use all available values recorded during Weeks 1-2, 3-4, 5-6 and 7-8. Missing data are not directly imputed in this analysis; however, all non-missing data for a subject will be used within the analysis to estimate the treatment effect for the mean number of Inhalations of rescue medication over Weeks 1-8. Two models will be fitted; one with a response variable of mean number of Inhalations. The variance-covariance matrix will be assumed unstructured.

Estimated treatment differences for UMEC/VI vs. TIO/OLO will be presented together with 95% confidence intervals (CIs) for the difference and p-values.

The percentage of rescue-free days will be analysed similarly. If the assumption for normality is not satisfied a non-parametric analysis will be used instead. Full details will be given in the RAP.

The CAT endpoint at Week 4 and Week 8 will be analysed using an MMRM analysis as described for the primary endpoint of trough FEV_1 .

Responder analyses for trough FEV_1 and CAT will be analysed using a logistic regression analysis for Week 4 and Week 8 separately. Further details will be given in the RAP.

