2.3. Study Design

2.4. Statistical Hypotheses

The null hypothesis is that the difference in trough FEV_1 between treatment groups is less than or equal to a pre-specified non-inferiority margin Δ :

H₀: $T_1 - T_2 \leq \Delta$

The alternative hypothesis is that the difference between treatment groups is greater than the margin.

 $H_1: T_1 - T_2 > \Delta$

where T_1 and T_2 are the treatment means for UMEC/VI 62.5/25 mcg and TIO/OLO 5/5 mcg, respectively.

CONFIDENTIAL

The non-inferiority margin has been set at -50mL, which is consistent with the noninferiority margins used for trough FEV_1 or 0 to 24 hour weighted mean FEV_1 in previous studies comparing long-acting bronchodilators or long-acting bronchodilator/ICS combinations [Ichinose M, 2010; Vogelmeier C, 2010; Agustí A, 2014].

If the lower bound of the two-sided 95% confidence interval around the (UMEC/VI 62.5/25 mcg vs. TIO/OLO 5/5 mcg) treatment difference is above -50mL then UMEC/VI 62.5/25 mcg will be considered non-inferior to TIO/OLO 5/5 mcg.

If the lower bound of the two-sided 95% confidence interval around the (UMEC/VI 62.5/25 mcg vs. TIO/OLO 5/5 mcg) treatment difference is above 0 then UMEC/VI 62.5/25 mcg will be considered superior to TIO/OLO 5/5 mcg.

P-values will be displayed in the analysis outputs in this study. Inference to be drawn from these p-values will be as follows:

- If the treatment comparison on the primary endpoint has a lower confidence limit below the non-inferiority margin, non-inferiority is not demonstrated. No inference will be drawn from p-values for treatment comparisons on any other endpoints.
- If the treatment comparison on the primary endpoint has a lower confidence limit above the non-inferiority margin but below 0, non-inferiority is established but the p-value cannot be used to give an indication of the strength of that noninferiority. Note the p-value is for a test of superiority and not associated with a test for non-inferiority.

Inference will be drawn from p-values for treatment comparisons on non lungfunction related endpoints (see below), which will be called statistically significant if <0.05. If the treatment comparison on the primary endpoint has a lower confidence limit above 0, superiority is established and the p-value can be used to give an indication of the strength of that superiority. Inference will be drawn from p-values for treatment comparisons on all other endpoints, which will be called statistically significant if <0.05.

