<pre>proc glimmix data=start; class subject period treatment visit; model endpoint(descending)=period treatment visit mean_base period_base visit*period_base visit*mean_base visit*treatment / dist=binary link=logit ddfm=kr solution; random intercept / subject=subject; random visit / subject=subject*period residual type=un; lsmeans visit*treatment / diff; ods output lsmeans=lsmeans; ods output diffs=diffs; run;</pre>
Note: The residual statement turns the random statement into a repeated statement
Model Checking & Diagnostics
Refer to Appendix 11: Model Checking and Diagnostics for Statistical Analyses.
Model Results Presentation
The odds ratio, 95% CI and p-value of UMEC/VI 62.5/25 vs. TIO/OLO 5/5 will be presented.
Summary Results Presentation
The number and percentage of responders and non-responders at each visit will be summarized on the same table as the analysis results detailed above.

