8.1.2.5. E-RS

Sta	Statistical Analyses for E-RS						
En	Endpoints						
•	Change from baseline in weekly mean scores for E-RS and its subscales (breathlessness, cough and sputum and chest symptoms)						
Мо	Model Specification						
•	E-RS endpoint above will be analyzed using similar methodology as the MMRM analysis of Trough FEV ₁ (detailed in Section 7.1.2) using all available data recorded from the EXACT-PRO questionnaire.						

• For E-RS and subscales, all weekly mean scores will be included in the analysis. Model Checking & Diagnostics

Sta	atistical Analyses for E-RS
•	Refer to Appendix 11: Model Checking and Diagnostics for Statistical Analyses.
Мо	odel Results Presentation
•	Least squares (LS) mean and LS mean changes from baseline with their corresponding standard errors (SEs) will be presented for each treatment by weekly treatment period, together with estimated treatment differences (UMEC/VI 62.5/25 vs. TIO/OLO 5/5), corresponding 95% CIs and p-values.
Su	mmary Results Presentation
•	The mean score at baseline and during each week of treatment will be summarized by treatment. The change from baseline values will also be summarized by treatment, for each week of treatment.
Sta	atistical Analysis of Proportion of Responders according to E-RS
En	dpoints
•	Proportion of responders for E-RS and its subscales (breathlessness, cough and sputum and chest symptoms)
Мо	odel Specification
•	For each mean weekly E-RS total score and subscales, the proportion of responders will be analyzed using similar methodology as the generalized linear mixed model analysis of Trough FEV ₁ responder (detailed in Section 8.1.2.1).
•	Please see Section 10.6.4 for details on responder definitions.
•	See Section 10.7.2 for details on how to handle missing data.
Мо	odel Checking & Diagnostics
•	Refer to Appendix 11: Model Checking and Diagnostics for Statistical Analyses.
Мо	odel Results Presentation
•	The odds ratio, 95% CI and p-value of UMEC/VI 62.5/25 vs. TIO/OLO 5/5 will be presented
Su	mmary Results Presentation
•	The number and percentage of responders and non-responders at each visit will be summarized on the same table as the analysis results detailed above.

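### The responder models put a free residual covariance on yes/no data as well as a random subject effect, so their 5% tests tend to reject too often

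*SAP*

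**What the plan says.** Protocol 9.4.1 planned the FEV1 and CAT responder endpoints as a "logistic regression analysis for Week 4 and Week 8 separately", with further detail left to the analysis plan.

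SAP 8.1.2.1 replaces this with one generalised linear mixed model across both visits. The model bullets list the fixed effects but no covariance structure; that appears only in the example code. The code sets "dist=binary link=logit ddfm=kr solution" and then "random intercept / subject=subject; random visit / subject=subject*period residual type=un". A note shows that the second layer is deliberate: "The residual statement turns the random statement into a repeated statement". The code names no estimation method and no empirical standard error.

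SAP 8.1.2.4 has the same line for CAT responders ("random visit / subject=subject*period residual type=un"). For E-RS responders, SAP 8.1.2.5 has weekly scores "analyzed using similar methodology as the generalized linear mixed model analysis of Trough FEV ₁ responder".

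Each model reports an odds ratio, 95% CI and p-value. SAP 2.4 allows inference from p-values on other endpoints, "which will be called statistically significant if <0.05", subject to the primary result. SAP Appendix 11 restricts model checking to the non-binary MMRM analyses. SAP Table 1 does not list the change of responder method.

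**The concern.** The covariance statements match those of the primary MMRM in SAP 7.1.2. There the outcome is continuous, so a residual variance is a genuine free parameter. A binary outcome with conditional probability p has variance p(1 − p) and nothing left to estimate. The unstructured block estimates a scale for each visit anyway. Under pseudo-likelihood, which GLIMMIX uses when no method is named, the predicted subject effects absorb part of the binary noise, the scale falls below 1, and the model standard errors shrink with it.

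If so, the confidence intervals for the responder odds ratios are too narrow, and results may be called significant at an error rate above the stated 5%. No planned diagnostic would show it.

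**Working it through.** **The plan's own figure.** The documents give no operating characteristic for the responder models beyond the nominal 0.05. The nearest checkable figure is the sample size in Protocol 9.2.1, which supplies the within-subject SD used below. SE of the difference = 140 × √(2/168) = 15.28 mL; 50/15.28 = 3.273; 3.273 − 1.960 = 1.313; power = Φ(1.313) = 0.905. The stated 90% is reproduced, so 140 mL is the SD of a single within-subject value.

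**Inputs from the documents.** Within-subject SD 140 mL, or 113 mL from one earlier study (Protocol 9.2.1); 186 ITT subjects with Week 8 data (Protocol 9.2.1); two periods with two visits each; responder if change is at least 100 mL (SAP 10.6.4); fixed effects and covariance as in SAP 8.1.2.1.

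**Assumed.** Between-subject SD of the FEV1 change, correlation within a period, and response rate (34 to 69% in set 2).

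**Method.** Data were generated with no treatment difference. The SAP model was fitted by residual subject-specific pseudo-likelihood, programmed in Python because SAS was not available. In sets 1 and 2 the Week 8 treatment contrast was tested with a fixed critical value of 1.973 in place of Kenward-Roger degrees of freedom.

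| Set | Scenario | Null rejection | Model SE / actual SD |
|---|---|---|---|
| 1 (190 subjects) | between-subject SD 100 mL, within 140 | 6.1% (722 runs) | 0.94 |
| 1 | 150 mL, within 140 | 7.1% (590) | 0.86 |
| 1 | 200 mL, within 113 | 13.9% (481) | 0.75 |
| 2 (186) | lowest correlation | 6.0% (600) | 1.02 (median SE) |
| 2 | no between-subject SD in response | 7.6% (1000) | 0.91 |
| 2 | weak to moderate correlation, about 52% responders | 8.6%, 9.0%, 9.3% | – |
| 2 | 34% responders | 12.7% | – |
| 2 | 69% responders | 15.2% | – |
| 2 | between-subject SD 200 mL | 16.3% | 0.65 (median SE) |
| 2 | extreme: SD 300 mL, correlation 0.7 | 21.8% | – |
| 3 (186, within 140) | between-subject SD 50, 100, 150, 200 mL | 7.0%, 7.6%, 10.8%, 13.8% (500 each) | 0.93 down to 0.69 (median SE) |

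Monte Carlo standard errors are about 0.7 to 1.6 points.

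**Mechanism.** The residual variances were estimated at about 0.5 to 0.8 in set 1, 0.4 to 0.8 in set 2 (0.95 at the lowest correlation), and 0.81 down to 0.57 in set 3, instead of 1.

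**Do the two columns agree?** If the standard error is r times the true SD, a normal approximation gives rejection 2 × [1 − Φ(1.973 × r)]:
- r = 0.94: 1.973 × 0.94 = 1.855, giving 6.4% (observed 6.1%).
- r = 0.75: 1.480, giving 13.9% (observed 13.9%).
- r = 0.69: 1.361, giving 17.3% (observed 13.8%).

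The shrunken standard error accounts for the size of the inflation, if not exactly.

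**Alternatives with no treatment difference.**
- GEE logistic, robust SE (set 1 data): 4.8%, 4.6%, 2.9%.
- SAP model with a subject-level sandwich SE (set 2 data): 4.3 to 7.4%.
- Residual line deleted, pseudo-likelihood kept (set 1): 0.4 to 3.7%. Adding a subject-by-period intercept (set 2): 0.9 to 3.9%.
- Random intercept deleted: 1.0 to 3.4% in set 3, where correlation between periods is then ignored. A marginal fit in set 2 gave 3.2 to 6.1%, but it reports four covariance parameters, one more than a 2 × 2 block has, so it appears to have kept a between-period term.

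**The case against.** **It is only example code for supportive endpoints.** The bullets prescribe no covariance, the trial is sized on the primary endpoint, and SAP 2.4 restricts inference. Most of this stands and lowers the priority. But the code is the only place where the covariance is stated, so it is what would be run.

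**The range is not a property of the plan.** This stands. No document gives the between-subject SD, correlation or response rate. The 6.1% result (44 of 722) has an exact 95% interval of 4.5 to 8.1% and the 6.0% result (36 of 600) one of 4.2 to 8.2%; neither is distinguishable from 5%. The 13.9% case in set 1 changes two inputs at once. Yet with the design SD of 140 mL throughout, set 3 gives 10.8% (54 of 500; 8.2 to 13.9%) and 13.8% (69 of 500; 10.9 to 17.1%), which chance does not explain.

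**Kenward-Roger might repair it.** No run used GLIMMIX or the full adjustment. Widening the set 1 standard errors by 2% as a rough allowance still gives 5.5%, 6.8% and 13.1%.

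**Stronger readings a reader might infer.**
- That standard errors are always too small. At the lowest correlation the ratio was 1.02, and in some scenarios a few unstable fits pulled the mean SE up; up to 24% of fits in set 2 needed more than 20 outer iterations.
- That E-RS is worse because eight weekly scores imply an 8 × 8 block with 8 × 9/2 = 36 parameters. SAP 8.1.2.5 says only "similar methodology as the generalized linear mixed model analysis", so the block is an inference, and neither it nor the CAT model was simulated.
- That the primary result is compromised. It is not: that model is for a continuous outcome.
- That the unlogged change is a serious departure. The protocol left detail to the analysis plan, and the joint model still gives a result per visit, so this is a documentation gap.

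**Conclusion.** The responder code is wrong as written and should be fixed. Putting a free residual covariance on binary data on top of a random subject intercept tends to make the standard errors too small and the 5% test anti-conservative. For the two-visit FEV1 case the null rejection rate was about 6 to 16% across plausible assumptions, near 5 to 6% at low correlation, with 21.8% in one extreme case outside that range. These figures rest on assumed between-subject SD, correlation and response rate, complete data in the 186-subject runs of set 2, and a Python implementation without full Kenward-Roger. For CAT and E-RS only the shared specification is established, not the size.

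The reach is limited. Under SAP 2.4, E-RS responders, and CAT responders if read as part of the CAT score, are open to inference once non-inferiority is shown. FEV1 responders are open only after superiority, and the sample size assumes a true difference of 0 mL. If non-inferiority fails, no inference is drawn on any of them.

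**What to change.** In SAP 8.1.2.1, 8.1.2.4 and 8.1.2.5, state the covariance approach in the text and replace both RANDOM statements with one of these:

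1. Preferred: a GEE logistic model with the same fixed effects, subject as the cluster, robust standard errors, and visit-specific odds ratios from the visit-by-treatment contrast.
2. If a subject-specific odds ratio is wanted: random intercepts for subject and for period within subject, fitted by quadrature, with no residual statement. This option was not simulated and should be checked first.

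Do not simply delete one of the two RANDOM lines under pseudo-likelihood: both reduced versions can be conservative. Reverting to the protocol sentence alone is not enough either, since it does not say how a subject's two periods are to be linked.

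Record in SAP Table 1 the change from separate-visit logistic regression. For E-RS, say explicitly how the weekly scores enter.

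The cost is SAP wording and code only. The GEE odds ratio is population-averaged, so somewhat closer to 1, and GEE needs a stronger missing-data assumption. SAP 10.7.2 limits this by counting subjects with no later assessment as non-responders, but it leaves intermittent gaps and missing baselines as missing. GEE may also be slightly conservative: its 2.9% (14 of 481) has an exact 95% interval of 1.6 to 4.8%.

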8.1.2.2. Trough FVC and IC

Statistical Analyses

Endpoints

- Trough FVC
- Trough IC

Model Specification

 Trough FVC and Trough IC endpoints above will be analyzed using the same methodology as the primary analysis of trough FEV₁ (detailed in Section 8.1.2.1) using all available FVC or IC data recorded at Weeks 4 and 8.

Model Checking & Diagnostics

• Refer to Appendix 11: Model Checking and Diagnostics for Statistical Analyses.

Model Results Presentation

- Least squares (LS) mean and LS mean changes from baseline with their corresponding standard errors (SEs) will be presented for each treatment by visit, together with estimated treatment differences (UMEC/VI 62.5/25 vs. TIO/OLO 5/5), corresponding 95% CIs and pvalues.
- A plot of LS mean changes from baseline and 95% CIs for each treatment by visit will be generated.

Summary Results Presentation

- Summary of baseline FVC will be presented by treatment for all subjects.
- Summary statistics for raw and change from baseline in trough FVC at each visit and for each treatment will be presented on the same table.
- Summary of baseline IC will be presented by treatment for all subjects.
- Summary statistics for raw and change from baseline in trough IC at each visit and for each treatment will be presented on the same table.

8.1.2.3. Rescue Medication

Mean number of Puffs/Occurrences of Rescue Medication Endpoints

- Mean number of puffs per day of rescue medication over the study duration (Weeks1-8) captured using e-diary
- Percentage of rescue-free days over the study duration (Weeks 1-8) captured using e-diary

Ме	an number of Puffs/Occurrences of Rescue Medication
٠	Mean number of occurences per day of rescue medication over the study duration (Weeks1-8)
	captured using e-MDI
•	Percentage of rescue-free days over the study duration (Weeks 1-8) captured using e-MDI
Мо	del Specification for MMRM Analysis Weeks 1-8
٠	Each endpoint derived for Weeks 1-2, 3-4, 5-6 and 7-8 will be analysed using a MMRM
	analysis using all available values recorded during Weeks 1-2, 3-4, 5-6 and 7-8.
•	The following covariates will be included in the model: period baseline, mean baseline, period,
	treatment, two-weekly period, two-weekly period by period baseline interaction and two-weekly
	period by mean baseline interaction.
•	The overall treatment effect will be estimated.
•	Two models will be fitted for each endpoint; one with a response variable of mean number of
	puffs/day or percentage of rescue-free days, and one with a response variable of the change
	from baseline.
•	An unstructured covariance structure for the R matrix will be used by specifying 'type=UN' on
	the REPEATED line.
•	The Kenward and Roger method for approximating the denominator degrees of freedom and
	correcting for bias in the estimated variance-covariance of the fixed effects will be used.
Ex	ample SAS code
	proc mixed data=start:
	class subject period treatment 2wkperd:
	model endpoint=period treatment 2wkperd mean base period base
	2wkperd*period base 2wkperd*mean base /
	ddfm=kr:
	random intercept / subject=subject:
	repeated 2wkperd / subject=subject*period type=un:
	Ismeans treatment / cl diff e :
	ods output Ismeans=Ismeans:
	ods output diffs=diffs:
	run:
Мо	del Checking & Diagnostics
•	Refer to Appendix 11: Model Checking and Diagnostics for Statistical Analyses
Mo	del Results Presentation
	The LS mean and LS mean change from baseline over Weeks 1-8 with their corresponding
•	Ses will be presented for each treatment together with the estimated treatment difference
	(IMEC/VI 62 5/25 vs. $TIO/OI O 5/5$) corresponding 95% CI and p-value
•	Percentage of rescue-free days will have LS mean with over Weeks 1-8 with their
•	corresponding SEs will be presented for each treatment, together with the estimated treatment
	difference (LIMECIVI 62.5/25 vs. $TIO/OL O.5/5$), corresponding 0.5% CL and p value
C	mmany Results Presentation
Ou	The mean number of nuffe of receive medication per day at baseline, during each two weeks of
•	treatment and over the optice 8 week treatment period will be summarized by treatment. The
	abange from baseline values will also be summarized by treatment, for each two weeks of
	treatment and the entire 8 week treatment period
-	This will be reported for percentage of readule free days
•	This will be repeated for percentage of rescue-free days.
•	Unly the above summaries (not analysis) will be repeated for rescue medication

Mean number of Puffs/Occurrences of Rescue Medication

(albuterol/salbutamol) collected using eMDI.

Non-parametric analysis

• If the assumption of normality is not satisfied (as seen in previous studies with similar design), a non-parametric analysis will be carried out. Hodges Lehman estimates for the median treatment difference and 95% confidence interval based upon a Wilcoxon rank sum test will be used. The p-value will be based on Van Elteren test, an extension to the Wilcoxon rank sum test for two group comparison.

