8.1.2.6. Inhaler assessment summaries

Inh	Inhaler Error Assessment							
En	dpoint							
•	Percentage of subjects making at least one critical error							
•	Percentage of subjects making at least overall error							
•	See Section 10.6.4 for error derivation.							
Su	Summary of Results Presentation							
٠	Summarized by inhaler, response (at least one error critical and overall) using n and %.							
	Results will be presented by sequence and total.							
•	The number and percent of subjects reporting each error for each individual question will also be presented (separate table for each inhaler).							

Sta	itistical Analysis of Inhaler Ease of Use Assessment
En	dpoints
•	Ease of use' rating for the ELLIPTA DPI compared with the Respimat.
Мо	del Specification
•	Each question will be analysed using the Cochran-Mantel-Haenszel test adjusted for country The Cochran-Mantel-Haenszel test serves as a stratified approximation to Prescott's test a
•	variation of a one-sample chi-square test that accounts for study inhaler sequence and difference in ease of use response [Prescott, 1981; Senn, 2002]. Homogeneity among country with respect difference in to ease of use will be assessed using a Breslow-Day test. Results of this test will not be reported on the final data display. See Section 10.6.4 for ease of use derivation.
Exa	ample SAS code
•	SAS code for stratified approximation to Prescott's test for each preference question:
•	ods output CMH = cmhi (where = (upcase(AltHypothesis) =: 'ROW MEAN SCORES') keep = AltHypothesis Prob) ; proc freq data = pref_data ; tables country * seq * ease_ord / cmh ;
	run ;
•	SAS code for checking brestow-Day rest for 2x2
	proc freq data = pref_data (where = (ease_ord ne 0)) ; tables country * seg * ease_ord / cmb :
Мо	del Results Presentation
•	P-values will be presented for the comparison between inhalers on the summary table
Su	mmary Results Presentation
•	Responses to the Ease of Use questionnaire will be summarised by inhaler, question/item
	and type of responses for the IN population.
•	The percentage preference (rated higher for Ellipta, rated higher for Respimat, rated the same) will be summarized on the same table as the analysis results detailed above. Results will be
	presented by question, sequence and total.
•	An additional summary will be produced based on the difference between the ratings for
	the two inhalers. The rating are coded as Very Easy=1, Easy=2, Neutral=3, Difficult=4,

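### The non-parametric fallback for e-diary rescue use is a two-group rank method that ignores the crossover pairing and names no stratum, so its stated 5% and 95% levels are not what it would deliver

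*SAP*

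**What the plan says.** SAP 8.1.2.3 names two e-diary endpoints over Weeks 1-8: puffs per day and percentage of rescue-free days. The planned analysis is a repeated measures model on two-weekly values. It respects the crossover: "The following covariates will be included in the model: period baseline, mean baseline, period" and others, with "random intercept / subject=subject" in the example code. Two versions are fitted, one on the value itself "and one with a response variable of the change" from baseline.

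If normality fails ("as seen in previous studies with similar design"), the fallback applies: "Hodges Lehman estimates for the median treatment difference and 95% confidence interval based upon a Wilcoxon rank sum test will be used". The p-value comes from a Van Elteren test, described as "an extension to the Wilcoxon rank sum test for two group comparison". The SAP gives no code, no stratum, and no choice between value and change. Protocol 9.4.1 leaves the detail to the RAP, which is this SAP. SAP 10.8.1 rules centre out of the statistical analyses, so centre is not an implied stratum.

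For inhaler ease of use, by contrast, SAP 8.1.2.6 specifies a crossover comparison: "Each question will be analysed using the Cochran-Mantel-Haenszel test adjusted for country", tabulated as "country * seq * ease_ord", that is, by sequence within country.

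**The concern.** The rank-sum test and its interval assume that the two groups are independent. Here the same people are in both groups, so the variance used is not the variance of the comparison. Whether it is too large or too small depends on which response is ranked, and the SAP does not say. Van Elteren is a stratified test and cannot be run as specified until a stratum is chosen.

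The SAP itself reports that normality failed in similar studies, so the fallback may well be used. Under SAP 2.4, rescue use is one of the endpoints on which p<0.05 may be called significant once non-inferiority is shown. At stake are the true size of that test, the coverage of the reported interval, and an analysis choice left open in an open-label trial.

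**Working it through.** **Inputs.** The design is a two-period crossover with equal allocation to two sequences (Protocol 4.1, 6.3). The number of complete pairs is taken as 186, the ITT subjects expected to have a Week 8 assessment (Protocol 9.2.1). The protocol's chain is consistent: 168/0.90 = 186.7 and 186/0.85 = 218.8, against 186 and 220 stated. No error rate, power or correlation is given for rescue use, so there is no plan figure to reproduce. Correlations of 0.3, 0.5 and 0.7 between a subject's two period values are assumed.

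**Step 1: raw values grouped by treatment.** With correlation ρ, the true variance of the treatment contrast is (1 − ρ) times what the two-group method assumes. Approximate size is therefore 2Φ(−1.96/√(1 − ρ)).

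- ρ = 0.3: 1.96/0.837 = 2.34, size 1.9%
- ρ = 0.5: 1.96/0.707 = 2.77, size 0.6%
- ρ = 0.7: 1.96/0.548 = 3.58, size 0.03%

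**Step 2: change from period baseline.** Order the four measurements as B1, O1, B2, O2 (baseline and outcome in each period), with unit variances. The covariance of the two changes is cov(O1,O2) − cov(O1,B2) − cov(B1,O2) + cov(B1,B2).

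- Equal correlations: ρ − ρ − ρ + ρ = 0. The changes are uncorrelated and size is about 5%.
- Decay by a factor r per step: r² − r − r³ + r² = −r(1 − r)². Each change has variance 2(1 − r), so the correlation is −r(1 − r)/2. It is negative, so the assumed variance is too small. With r² = 0.3, 0.5, 0.7 (r = 0.548, 0.707, 0.837) the correlation is −0.124, −0.104, −0.068. Size is 2Φ(−1.96/√1.124) = 6.4%, then 6.2% and 5.8% by the same formula.

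**Step 3: simulation on skewed data.** There were 20,000 null trials per cell with 186 pairs and no period effect. Margins were lognormal, or zero-inflated with 30% zeros; correlations were equal or decaying. True size at nominal 5%:

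| Reading | ρ = 0.3 | ρ = 0.5 | ρ = 0.7 |
|---|---|---|---|
| Raw, by treatment, unstratified | 1.9-2.2% | 0.6-0.9% | 0.05-0.1% |
| Raw, Van Elteren by period | 1.9-2.2% | 0.5-0.9% | 0.05-0.1% |

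Results over all three correlations:

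- Change, by treatment: 4.8-5.2% with equal correlations, 5.3-6.1% with decay.
- Van Elteren by subject: 4.4-5.1%.
- Period differences compared by sequence: 4.8-5.2% for either response.

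Keeping 33 of 220 subjects with Period 1 only gives 2.2-2.5%, 0.9-1.1% and 0.1-0.2% on raw values by treatment, and 4.7-6.6% on change.

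A separate simulation added a period effect of 0.3. Van Elteren by subject then fell to 2.1-4.1%, lowest at the highest correlation. The sequence comparison stayed at 4.7-5.5%.

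**Step 4: intervals.** Normal and lognormal data, 1,500 trials per cell. The by-treatment 95% interval covers 97.5-100% on raw values and 93.5-96% on change. The sequence-based interval covers 94-96.5%. The width ratio (by-treatment over sequence-based) is 0.84-1.81 on raw values and 0.78-1.00 on change.

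**Step 5: why halve.** With treatment effect τ and period effect π, the mean of Period 1 minus Period 2 is π + τ in one sequence and π − τ in the other. The shift between sequences is 2τ and π cancels. Unhalved, a true 0.20 is estimated as 0.40, and coverage falls to 77% at ρ = 0.3 and 35% at ρ = 0.85.

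**The case against.** The best defence is that the section is less open than it looks. The endpoints are named, the estimate is described as a difference between treatments, and on that reading with raw values false positives are over-controlled. Rescue use is an 'other' endpoint, the fallback is conditional, and eMDI data are only summarised. All of this stands and limits the point. It does not rescue the method: a nominal 5% test with a true size of 2% or far less, and a 95% interval covering up to 100%, are not what the SAP says it reports.

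Four stronger readings are tempting, and the documents do not support them.

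- *Response, grouping and stratum are all missing.* Only the stratum is wholly absent.
- *The SAP's silence alone moves size from about 0.1% to 6%.* Much of that span comes from the assumed correlation: the same raw-value reading gives about 2% at 0.3 and 0.1% or less at 0.7.
- *The fallback inflates false positives badly.* Ranking two-weekly records by treatment did reach 10.6-12.6% at the lowest correlation simulated. But the endpoints and the SAP 10.13.5 analysis titles are for Weeks 1-8.
- *It loses power or gives wider intervals.* On raw lognormal data at correlation 0.3 the by-treatment interval is the narrower one (ratio 0.84-0.85), and on change it is never wider. No general loss can be claimed for the skewed data on which the fallback would be used.

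**Conclusion.** The point holds. The fallback is a two-group method in a crossover. Its Van Elteren stratum is unnamed, and raw value or change is not chosen. Grouped by treatment on raw values, it is conservative with an over-covering interval: about 2% size at correlation 0.3, under or about 1% at 0.5, and about 0.1-0.2% or less at 0.7. On change from baseline it is near nominal, or about 5-7% under decaying correlation. Van Elteren by subject remains valid but becomes conservative with a period effect, and the accompanying rank-sum interval would still ignore pairing.

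All sizes rest on assumed correlations and distributions. Interval coverage was not checked on zero-inflated data or on a percentage bounded at 0 and 100, so it is not shown for rescue-free days. The consequence is confined to an 'other' endpoint. The change should still be made, because the p-value carries inference and a crossover-valid version is readily available.

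**What to change.** In SAP 8.1.2.3, before database freeze:

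1. Name the response: Weeks 1-8 value or change from that period's baseline.
2. Take each subject's Period 1 minus Period 2 difference and compare the two sequences with the Wilcoxon rank-sum test. SAP 10.6.4 already defines Weeks 1-8 values per period.
3. Report half the Hodges-Lehmann shift and half its confidence limits, signed as UMEC/VI minus TIO/OLO.
4. Drop Van Elteren, or apply it to these differences with a named between-subject stratum. Country is one option, as in SAP 8.1.2.6; with five assumed country strata, simulated size was 4.7-5.3%.

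The cost is two or three sentences and a small program change. There are three downsides. Subjects with only one period drop out of the fallback (up to 15% of 220, or 33), which departs from the use of all available values in the main model. The period-baseline and mean-baseline covariates are not carried. The interval can be wider than the by-treatment one on strongly skewed raw data with low correlation, or on change from baseline.
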